9.2 Pharmacodynamics

The analysis of PD data will be performed on the PD-PPS. All listings will be presented for the SS.

9.2.1 Total Serum IgG

Total Serum IgG concentrations and IgG subclasses will be listed by treatment group and timepoint including absolute changes from Baseline and percentage changes from Baseline. Descriptive summaries (including n, arithmetic mean, median, SD, minimum and maximum) will be presented by treatment group and timepoint and ADA status (6 categories; see Section 9.3.2) for absolute values, changes from Baseline and percentage changes from Baseline.

Study participant total Serum IgG will be plotted against planned time. Mean Serum IgG, mean change from Baseline and percentage change from Baseline will be plotted against planned time by treatment group.

For each study participant, the minimum value and maximum decrease (absolute and percentage) from Baseline in total serum IgG concentration during the study (using all available data up to cut-off point) will be listed. The minimum value and maximum decrease will be summarized by treatment group. If a decrease from Baseline in IgG is not observed in a given study participant, the maximum decrease will be reported as the smallest increase from Baseline.

9.3 Immunological analyses

All analyses described in this section will be based on the SS.

9.3.1 Immunoglobulins

Immunoglobulins (IgA, IgE and IgM) will be listed by timepoint including changes from Baseline. Descriptive summaries will be presented by timepoint for both absolute values and changes from Baseline.

Individual figures over time (absolute value) will be presented by study participant, with all variables overlaid on the same plot and separate plots each study participant.

Any values that are BLQ or ALQ will be handled as described in Section 4.2.4.

9.3.2 Anti-drug antibodies

Anti-rozanolixizumab antibodies will be measured using a three-tiered assay approach: screening assay, confirmatory assay and titration assay. The results for the ADA measurements will be listed by treatment group and timepoint based on the SS, including the Screening assay, confirmatory assay and titer (if applicable).

Samples will first be evaluated in the screening assay using a false positivity rate of 5% (reported as negative screen or positive screen), followed by analysis of screened positive samples in the confirmatory assay (which is a drug depletion assay) to confirm the true positivity of the samples (reported as negative immunodepletion or positive immunodepletion). Samples that are confirmed as positive will be evaluated in a titration assay to quantify the ADA level and will be reported as titer (reciprocal dilution factor including minimum required dilution (MRD)).

Screening, confirmatory and titer cut points of the respective assays will be determined by the bioanalytical laboratory.

The ADA status should be determined for each visit where samples were taken for ADA analysis:

- Sample values that are either negative screen or positive screen and negative immunodepletion will be defined as ADA negative
- Sample values that are positive screen and positive immunodepletion will be defined as ADA positive.

There will be six study participant classifications:

1. For study participants who are negative at baseline, and antibody negative at all sampling points post treatment (including FV)- pre ADA negative- treatment induced ADA negative

2. For study participants who are negative at baseline, and antibody positive at any sampling point post treatment (including FV)- pre ADA negative- treatment induced ADA positive. If a study participant has a missing pre-treatment sample (either missing or insufficient volume) at baseline with one or more ADA positive post-treatment samples will be also classified as pre ADA negative- treatment induced ADA positive
3. For study participants who are positive at baseline, and antibody negative at all sampling points post treatment (including FV)- pre ADA positive- treatment reduced ADA
4. For study participants who are positive at baseline, and are positive at any sampling point post treatment (including FV) with titer values of the same magnitude as baseline (i.e. \leq than a predefined fold difference from the baseline value)- pre ADA positive - treatment unaffected ADA
5. For study participants who are positive at baseline, and are positive at any sampling point post treatment (including FV) with increased titer values compared to baseline (above a predefined fold difference increase from baseline value which will be defined within the validation of the assay and will be included in the TFLs and/or SAP when available)- pre ADA positive- treatment boosted ADA positive.
6. For Study participants who have a positive pre-treatment sample and some post-treatment samples are missing, while other post-treatment samples are ADA negative, the study participant will be classed as inconclusive.

A study participant will be classified as having treatment-induced ADA positivity when meeting one of the following criteria:

1. The Baseline result is ADA negative and at least one post-Baseline timepoint is ADA positive
2. The Baseline result is ADA positive and at least one post-Baseline measurement shows a pre-defined fold increase in titer from the Baseline value (the fold increase from Baseline required to meet this criterion will be defined with the development of the assay and will be included in the TFLs)

A study participant will be considered:

- Overall ADA Positive if having at least one scheduled assessment that is confirmed positive during the treatment period (ie. classifications 2 to 6).
- Overall ADA Negative if having no scheduled assessments that are confirmed positive at any time in the treatment period (ie. classification 1).

The available ADA results will be listed. The listing will include rozanolixizumab concentration, ADA result (anti-rozanolixizumab antibody negative or positive), together with the confirmatory result (% inhibition) and ADA titer for results that are anti-rozanolixizumab antibody positive. In addition, the time since the previous administration of IMP will be reported (in days).

Number and percentage of ADA positive and negative study participants at the time of each visit and overall will be summarized by treatment group based on the SS.

The first occurrence of treatment-induced ADA positivity (based on the definitions above) will be summarized (number and percentage of study participants) at each post-Baseline visit, based

on the SS. This tabulation will count the number of study participants at each post-Baseline visit who fulfill at least one of the above defined criteria for treatment-induced positivity; study participants will be counted in the numerator based on the earliest visit at which one of these criteria is fulfilled. At other visits, study participants will be counted in the denominator (assuming a measurement is available). For all tabulations, percentages will be based on the number of observations at each visit.

The ADA status by the six categories, defined above, will be tabulated by treatment group, with an additional category "total treatment induced" combining study participants who are pre ADA negative- treatment induced ADA positive, study participants with a missing pre-treatment sample (either missing or insufficient volume) at baseline with one or more ADA positive post-treatment samples and study participants pre ADA positive- treatment boosted ADA positive.

The prevalence of immunogenicity, defined as (cumulative) proportion of study participants having positive immunodepletion ADA samples at any point up to and including that time point will be summarized by treatment group based on the SS. Missing samples will not be included in the denominator.

Individual plots of rozanolixizumab concentrations and ADA titer results as well as ADA titer results and percentage change from baseline in Total IgG by the six ADA classes described above will be presented. Spaghetti plots of ADA titer versus time will be presented for all ADA positive study participants based on the SS.

9.3.3 Serum complement levels and plasma complement levels

Serum (C3 and C4) and plasma (C3a and C5a) complement variables will be listed by treatment group and time point including changes from Baseline. Summaries using descriptive statistics will be presented by treatment group and by time point for both absolute values and changes from Baseline.

Any values are that BLQ or ALQ will be handled as described in [Section 4.2.4](#).

9.3.4 Cytokines

Serum cytokines will be listed by treatment group and by time point, changes from Baseline will be added to the listing. Summaries using descriptive statistics will be presented by treatment group and by time point for both absolute values and changes from Baseline, both for all study participants and for study participants experiencing infusion reactions.

Any values are that BLQ or ALQ will be handled as described in [Section 4.2.4](#).

9.3.5 CIDP-specific auto-antibodies

CIDP-specific auto-antibody sampling information captured in the eCRF will be listed. No results will be analyzed.

9.3.6 Tetanus-and influenza A virus-specific IgG antibodies

Tetanus-and influenza A virus-specific IgG antibodies will be listed by treatment group and time point. Summaries using descriptive statistics will be presented by treatment group and time point for both absolute values and changes from Baseline.

Any values are that BLQ or ALQ will be handled as described in [Section 4.2.4](#).

10 SAFETY ANALYSES

All safety analyses will be presented using the SS. Listings will be presented by treatment group and study participant; tabulations will be presented by treatment group and visit/timepoint (if applicable).

10.1 Extent of exposure

The initial dose administered will be based on the dose at the time of completion of the Treatment Period from the parent study (eg, CIDP01). For study participants who had a gap period between the parent study (eg, CIDP01) and CIDP04, a starting dose of [REDACTED] will be used (see protocol Table 7-1).

The intended dose will be calculated based on the study participant's weight at screening (where applicable) or Baseline in CIDP04 for Treatment Period Part 1. For Treatment Period Part 2, body weight is collected every 6 months starting at first visit in this period and the most recent weight will be used to select the correct volume for dose infusion from these timepoints. The calculation is done as follows for the applicable weight:

$$\text{Intended dose (mg)} = \text{weight (kg)} * [REDACTED]$$

The IMP solution contains [REDACTED] of rozanolixizumab. Actual dose in mg at Visit (i) will be calculated as follows:

$$\text{Actual dose at Visit (i) (mg)} = \text{Total actual volume delivered at Visit (i) (mL)} * [REDACTED]$$

where actual volume delivered is collected in eCRF, and in case of interruption it should be calculated as the sum of actual volumes delivered.

Overall exposure (%) will be calculated as mean exposure (%) at each visit as follows:

$$\text{Overall exposure (\%)} = \text{mean}([\text{Actual dose at Visit (i) (mg)} / \text{Randomized dose (mg)} - 1] * 100).$$

Overall exposure will be categorized as follows:

- < -10%
- $\geq -10\%$ and $\leq +10\%$
- $> +10\%$

The exposure categories will be used for the definition of the MFAS as well as the representation of Pharmacokinetic data ([Section 9.1](#)).

10.2 Adverse events

Adverse events will be recorded from the time of informed consent until study completion. All AEs will be coded ([Section 3.8](#)) and categorized by relationship to rozanolixizumab.

In addition, AEs will be classified according to the Common Terminology Criteria for Adverse Events (CTCAE) Version 5.0 for severity. For any AEs where it is not possible to provide a CTCAE grading, the events will be assessed using a standard intensity classification (mild, moderate and severe).

A TEAE is defined as any event that was not present prior the first administration of IMP in CIDP04 study or any unresolved event already present before the first administration of IMP in CIDP04 study that worsens in intensity following exposure to treatment until 8 weeks following

the last administration of IMP in CIDP04 study. Adverse events starting before the first administration of IMP in CIDP04 study or later than 8 weeks after the administration of the last IMP will not be considered TEAEs. Such events will be listed only.

Where dates are missing or partially missing, AEs will be assumed to be treatment-emergent unless evidence exists that does not allow the AE to be treatment-emergent. Handling of missing dates/times for classification of AEs as TEAEs is described in [Section 4.2.7](#).

The following rules will be used to assign a TEAE to the study periods:

- **Treatment Period:** a TEAE will be assigned to the Treatment Period for the tabulations if the start date/time of the event is at the time of or after the first administration of IMP in CIDP04 study on Week 1, up to Visit 26/PEOT (non-inclusively).
- **Observation Period:** a TEAE will be assigned to the Observation Period for the tabulations if the start date/time of the event is at or after Visit 26/PEOT till 8 weeks after administration of the last IMP in CIDP04 study.
 - The Observation Period's TEAEs will be stratified by TEAEs of study participants who received/did not receive standard of care treatment (i.e. Ig treatment) between start of the Observation Period and occurrence of the TEAE.

The number and percentage of study participants who experience TEAEs will be summarized by Treatment Period, Observation Period (standard of care treatment status identified by WHODD J06BA01 and J06BA02) and Overall, with respective treatment group. The following summaries will be presented:

- Incidence of TEAEs (overview including number and percentage of study participants with any TEAEs, serious TEAEs, discontinuations due to TEAEs, related TEAEs, TEAEs with CTCAE Grade 3 and above [or rated as 'severe' for events with no CTCAE classification], and deaths; event counts will also be included)
- Incidence of TEAEs by SOC, HLT and PT
- Incidence of TEAEs during the Dosing Period by SOC, HLT and PT
- Incidence of serious TEAEs by SOC, HLT and PT
- Incidence of non-serious TEAEs by SOC, HLT and PT
- Incidence of AEs of special interest by SOC, HLT and PT
- Incidence of AEs of interest by SOC, HLT and PT
- Incidence of TEAEs by relationship, SOC, HLT and PT
- Incidence of TEAEs by maximum relationship, SOC, HLT and PT
- Incidence of serious TEAEs by relationship, SOC, HLT and PT
- Incidence of non-serious TEAEs by relationship, SOC, HLT and PT
- Incidence of fatal TEAEs by relationship, SOC, HLT and PT
- Incidence of TEAEs by maximum intensity (mild, moderate and severe), SOC, HLT and PT

- Incidence of non-serious TEAEs above threshold of 5% of participants by SOC and PT
- Incidence of non-serious TEAEs above threshold of 5% of participants by relationship, SOC and PT
- Discontinuation due to AEs

Summary tables will contain counts of study participants, percentages of study participants in parentheses and the number of events. A study participant who has multiple events in the same SOC, HLT and PT will be counted only once in the study participant counts but all events will be included.

Adverse event summaries will be ordered by alphabetical SOC, alphabetical HLT within SOC and decreasing frequency in the treatment group.

In summaries including intensity, the CTCAE categories will be summarized according to the following categories:

- Grade 1: Mild
- Grade 2: Moderate
- Grade 3: Severe
- Grade 4: Severe
- Grade 5: Severe
- not gradable

In the case both category types are captured and the mapping to a standard intensity classification per above rule results in a class different from the standard intensity classification given in the eCRF, the worst case will be used.

These will be tabulated together with the AEs that were not classified according to CTCAE criteria i.e., all Grade 1 AEs as per CTCAE criteria will be included in the 'mild' category together with those AEs classified as mild as per the 'standard' intensity classification.

A listing will be presented by treatment group and study participant for all AEs. This will include the onset date/time and outcome date/time of the event (including relative days), the AE duration, days since first dose of IMP, days since most recent dose of IMP, actual dose received, study period, pattern of event, severity/intensity, relationship, action taken and outcome. In addition, the listing will flag AEs that led to discontinuation, TEAEs, serious adverse events (SAEs), AEs of interest, AEs of special interest and infusion reactions.

AEs of focus (ie, TEAEs that are a review focus for rozanolixizumab or the participant population) will be summarized, in separate tables, detailing all TEAEs meeting the following criteria described below:

- Headache using the UCB-defined search criteria.
- Gastrointestinal disturbances using the UCB-defined search criteria.
- Hypersensitivity reactions using the criteria SMQ='Hypersensitivity'

- Anaphylactic reactions using the criteria SMQ='Anaphylactic reaction' and the UCB-defined search criteria.
- Injection site reactions using the UCB-defined search criteria.
- Infusion reaction collected on the eCRF AE page.
- Opportunistic infections using the UCB-defined search criteria.
- Reductions in albumin and plasma proteins using the UCB-defined search criteria.
- Effects on the kidney using the criteria SMQ='Acute renal failure'
- Drug related hepatic disorders using the criteria SMQ='Drug related hepatic disorders - comprehensive search'.

For each of the above mentioned AEs of focus the following summaries will be presented:

- Incidence of all AEoFs by SOC, HLT and PT
- Incidence of all AEoFs by Relationship, SOC, HLT and PT
- Incidence of all serious AEoFs by SOC, HLT and PT
- Incidence of all AEoFs by Maximum Intensity, SOC, HLT and PT

UCB definitions for AEoF are found in a separate document "Adverse Events (AEs) of Focus for the rozanolixizumab Program" version 1.3, dated 04 Aug 2020.

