of Part 2). The Observation Period will not be performed in the event of a study participant continuing treatment with rozanolixizumab after the end of the study (ie, in case of an Access Program), in which case only the PEOT (Visit 26) Visit will be performed.

During the Treatment Periods (Part 1 and Part 2), study participants will have weekly visits (either on site or at home) during which they will be dosed with an sc infusion of rozanolixizumab up to [REDACTED]. The initial dose in the study will be based on the dose the study participant has received at the completion of the parent study (eg, CIDP01). For study participants who were known to be on placebo in the parent study, a starting dose of [REDACTED] will be used. The maximum dose will be [REDACTED]. See Section 7.2 for details on treatment to be administered.

During the first 4 weeks of the Treatment Period (Part 1), all visits will be on site. During Weeks 5 to 8, home visits and on-site visits will be alternating (Weeks 5 and 7 will be on site; Weeks 6 and 8 will be at home). Starting at Week 9 and through the end of the Treatment Period (Week 24 and if applicable, Week 76), study participants will have 1 visit on site followed by 3 visits at home for every 4-week period.

After the completion of the Treatment Period(s) (starting at Week 25 for study participants only completing Part 1 or from Week 77 for study participants completing both Part 1 and Part 2 or at any early timepoint in case of PEOT), study participants will enter the 8-week Observation Period where no IMP will be administered. During the Observation Period, study participants will have on-site visits at the entry and exit of the Observation Period (Weeks 25/77, and 32/84, and home visits at Weeks 27/79 and 29/81). Study participants can return to their SOC during the Observation Period. In case the study participant enters an Access Program, no Observation Period will be performed with the exception of the PEOT (Visit 26) Visit which will be immediately completed.

At the discretion of the investigator and/or study participant, home visits can be changed to site visits (eg, for safety reasons). In case an on-site visit cannot be performed, the next visit will be performed at site instead of at home, and all safety assessments that should have been completed at the missed visits will be performed.

The assessments to be completed during each visit are presented in Table 5-1.

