7.8.3 Rescue medication

If, at any time during this OLE study, a study participant relapses according to the predefined criteria for relapse as specified in Section [4.2.1](#) using the study participant's score on iRODS, INCAT, or maximum grip strength as assessed by the site personnel and supported by the medical judgement of the investigator, then rescue therapy must be considered and the study participant withdrawn from IMP (see Section [6.4](#)). The study participant will return to the SOC Ig treatment (eg, IVIg of 2g/kg) at the investigator's discretion.

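### The Observation Period TEAE split by Ig status reports participant percentages that do not measure risk within a stratum, and the SAP gives two different starts for the period

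*SAP*

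**What the plan says.** SAP 10.2 assigns a TEAE to the Observation Period "if the start date/time of the event is at or after Visit 26/PEOT till 8 weeks after administration of the last IMP". Those TEAEs are then stratified by whether the participant "received/did not receive standard of care treatment (i.e. Ig treatment) between start of the Observation Period and occurrence of the TEAE". The reporting unit is the participant: "The number and percentage of study participants who experience TEAEs will be summarized by Treatment Period, Observation Period", with Ig status identified by two WHODD codes, and "Summary tables will contain counts of study participants, percentages of study participants in parentheses and the number of events". The section names no denominator for the Observation Period columns or for either Ig stratum. The general rule in SAP 10 is "All safety analyses will be presented using the SS", and SAP 3.5.2 defines the Safety Set as everyone given at least one dose in CIDP04.

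Not everyone in that set has an Observation Period. Protocol 5.1 says "The Observation Period will not be performed in the event of a study participant continuing treatment with rozanolixizumab" after the study through an Access Program; SAP 2.3 repeats this.

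The start of the period is given in three places. SAP 10.2 (TEAEs) and SAP 6.4.2 (concomitant medication) start it at Visit 26/PEOT, that visit included. SAP 3.2.1.2 (study periods) starts it after the last IMP administration that precedes Visit 26/PEOT.

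On relapse, Protocol 7.8.3 requires that rescue be considered and IMP stopped: "The study participant will return to the SOC Ig treatment", at the investigator's discretion. Protocol 8.5 places the PEOT visit as near as possible to the withdrawal decision. SAP 4.2.1 foresees rescue before PEOT and deals with it for efficacy data only.

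**The concern.** The stratum is a property of the event, while the percentage is of participants. A participant with no TEAE has no event date against which to judge Ig, so the rule places them in neither stratum. A participant with one TEAE before Ig and another after it falls in both. No participant denominator specific to a stratum follows from such a rule. What remains is a common denominator (the Safety Set), with each column's count driven partly by how long participants spent in that state. Because participants may return to standard of care at any time in the period (Protocol 5.1), that split of time varies between them and is not accounted for.

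The two starts add a classification problem. Ig given after the last dose but before PEOT counts as received under one start and not under the other. A reader comparing off-drug events with and without Ig could see a difference where none exists, or find events that followed rescue Ig in the column for no Ig.

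**Working it through.** The plan states no figure on this point, so there is none to reproduce. All participant numbers, event rates and Ig timings below are assumptions for illustration.

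**1. Window.** Visit 26 is at Week 25 and the Final Visit at Week 32, so 32 − 25 = 7 weeks. After Part 2 it is 84 − 77 = 7 weeks.

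**2. Small example.** Assume 15 in a Safety Set group, 5 of whom go to an Access Program and 10 enter the period. Of these, 8 start Ig after 2 weeks and 2 never do. Three participants have a TEAE before Ig and 4 have one after, one event each.

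- On the Safety Set: 3/15 = 20.0% without Ig, 4/15 = 26.7% with Ig.
- On those who entered: 3/10 = 30% and 4/10 = 40%.
- Time without Ig: 8 × 2 + 2 × 7 = 30 person-weeks. Time with Ig: 8 × 5 = 40 person-weeks.
- Rates: 3/30 = 0.10 and 4/40 = 0.10 per person-week.

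The percentages differ and the rates do not. Access Program participants shrink both columns by the same factor (10/15), so they distort the level but not the ratio within a group.

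**3. Range, with no effect of Ig.** Let TEAEs occur at rate λ per week before and after Ig. Let time to first Ig be exponential with rate μ = ln 2 / median, and W = 7. Among participants who entered:

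- any TEAE before Ig = λ/(λ+μ) × [1 − e^(−(λ+μ)W)]
- any TEAE after Ig = [1 − e^(−μW)] − μ/(μ−λ) × e^(−λW) × [1 − e^(−(μ−λ)W)]

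Simulating 400,000 participants per row gave the values below. The formulas agree within 0.2 percentage points.

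| λ per week | Median weeks to Ig | Received Ig | Did not receive | In both |
|---|---|---|---|---|
| 0.05 | 2 | 19.2% | 11.8% | 1.4% |
| 0.05 | 4 | 13.1% | 17.7% | 1.2% |
| 0.10 | 2 | 33.8% | 21.5% | 4.9% |
| 0.10 | 4 | 23.3% | 31.2% | 4.0% |
| 0.20 | 2 | 53.7% | 35.8% | 14.2% |
| 0.20 | 4 | 37.4% | 49.8% | 11.7% |

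The order reverses at every rate when the median moves from 2 to 4 weeks. The cause is time at risk. Mean time before Ig is [1 − e^(−μW)]/μ. With a median of 2 weeks, μ = 0.3466, which gives 0.9116/0.3466 = 2.63 weeks before Ig and 7 − 2.63 = 4.37 after. Events per person-week returned the assumed λ in both strata to within 0.001.

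**4. Period start.** Take a participant given rescue Ig between the last IMP dose and PEOT.

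- Under SAP 3.2.1.2 that Ig lies inside the Observation Period and counts as received. Time misclassified: 0.
- Under SAP 10.2 it precedes the period. TEAEs are classed as without Ig until the next Ig.

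The documents give no interval between rescue and the next Ig. Assuming rescue 3 days (3/7 week) before PEOT and a next dose 2, 3, 4 or 6 weeks after rescue, the misclassified time is 1.57, 2.57, 3.57 or 5.57 weeks. That is 22%, 37%, 51% or 80% of a 7-week window. With weekly Ig it is 1 − 3/7 = 0.57 weeks, or 8%.

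**The case against.** The strongest reply is that SAP 10.2 stratifies events, so participants without events need no stratum, and one participant appearing in two columns is ordinary in adverse event tables. The Safety Set supplies a denominator, the same for both columns. The study is single-arm, no test between strata is planned, and onset and medication dates are listed, so any case can be traced. All of this stands. A reader might infer that no percentage can be formed at all; that goes too far, because a Safety Set percentage can be calculated. It simply does not describe risk with or without Ig. Percentages above 100% arise only from never-Ig and ever-Ig denominators, which the SAP does not propose.

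On rescue, SAP 6.4.2 assigns to the Observation Period any medication taken in it, including one started earlier, and PEOT should follow the withdrawal decision closely. This helps where Ig is recorded as one continuing entry. It does not help where a completed infusion precedes PEOT, and 10.2 still asks about Ig received after the start of the period.

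The 2- to 6-week interval comes from inclusion criterion 6. That is an entry rule for stable Ig, it also covers weekly SCIg, and it is not a rescue schedule. The 7-week window belongs to participants who completed treatment; a relapser's window runs from PEOT to 8 weeks after the last dose. The 80% figure is therefore only the top of an assumed range.

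**Conclusion.** The point holds as a fault in a descriptive table. Followed as written, the two Ig columns give percentages that do not measure risk within either stratum, and their difference can arise or reverse through the timing of Ig alone. How large this would be depends on assumed rates and timings; its direction cannot be known in advance.

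The rescue problem is conditional. It occurs under the Visit 26/PEOT start in SAP 10.2 and 6.4.2, affects only TEAEs before the next Ig, and disappears under SAP 3.2.1.2. A reader might infer that the SAP always files participants rescued before PEOT as untreated. The documents do not support that; they support a contradiction between sections that classifies the same participant in two ways.

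A reader might also infer that the primary safety variable is compromised. It is not: Overall and Treatment Period TEAE incidence do not use the Ig split. The change should be made, but the study's main safety result does not depend on it.

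**What to change.** 1. Use one Observation Period start in SAP 3.2.1.2, 6.4.2 and 10.2. If the last IMP dose is chosen, TEAEs between that dose and Visit 26/PEOT move out of the Treatment Period columns; keeping Visit 26/PEOT leaves them where they are.
2. In SAP 10.2, set Ig status from the first Ig after the last IMP dose, carrying forward Ig given before Visit 26/PEOT.
3. Limit the Observation Period columns to participants who entered that period, and state that number as the denominator.
4. For the two Ig strata, report participants with events, event counts and events per person-week. Start person-time where event counting starts, end it at the earlier of 8 weeks after the last dose and the end of follow-up, and split it at first Ig.
5. Do not compare participant percentages between strata. Even with denominators of those who entered and those who started Ig, the small example gives 3/10 = 30% versus 4/8 = 50% at equal rates.

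The cost is SAP wording and re-programming of the Observation Period columns in the TEAE summaries. SAP 10.2 lists 16, one of them confined to the dosing period. No new data are needed: medication dates (SAP 6.4) and event onset dates (SAP 10.2) are already collected.
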